Study Population	
Provider (OTs, SLPs, ATPs): 20
 
Caregivers of adult and pediatric patients: 20
 
Patients (adults and children): 20

Estimated # of Sites	Single Site: DESIN LLC will serve as the site and data will be gathered remotely and electronically using Qualtrics. Participants may reside anywhere in the United States. A description of the Qualtrics software and its capabilities, including data security features, is included later in this proposal.

Enrollment and Subject Participation Duration	
Staggered enrollment will occur over a 1- 3 month period. Participation in the study is approximately one week in duration including the trial of Obi Gen 3 and completion of the surveys. A follow-up semi-structured interview is optional and will not be conducted with all the participants. Follow-up interviews may be conducted with participants from any of the stakeholder groups whose responses require clarification or warrant further inquiry.

Primary Effectiveness Endpoint	
Assessment of user needs fulfillment after ~ one (1) week trial of Obi Gen3 using the following for each of the three (3) stakeholder groups as participants in the clinical investigation:
 
I.) Providers will complete - Survey specifically tailored to gather descriptive demographic data and inquire about their use experiences including whether their needs are fulfilled with the usability of Obi Gen3.
 
II.) Caregivers will complete - Survey specifically tailored to gather descriptive demographic data about the caregivers' use experiences and inquire about whether their needs are fulfilled with the Obi Gen3.
 
III.) Patients will complete: 1) Survey specifically tailored to gather descriptive demographic data about the patients' use experiences and inquire about whether their needs are fulfilled with Obi Gen3.

Primary Safety Endpoint	
Monitoring and recording of any adverse events through company's existing SOP120; None are anticipated due to the Class I device's low risk profile and the device's history of 0 adverse events.

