Study Procedure	
 1) Pre-screening by clinical staff per SOP220 to identify potential subjects who would likely meet the criteria for participation in the study. 2) Recruitment Flier is provided electronically and/or hard copy is mailed out with trial Obi Gen3 Medical Robot with triadic recruitment strategy (Provider, Caregiver, Patient) 3) Screening: In-office assessment performed by provider to determine eligibility for home/community trial per Standard Operating Procedures (SOP220) that would be completed regardless of whether participating in the study. While this is not specific to the study procedure, it has been included here to help clarify the process. 4) Informed consent will be obtained for all stakeholders interested in participating (Provider, Caregiver, Patient) electronically using Qualtrics 5) ~ One (1) week home/community trial of Obi Gen 3 with a minimum of a five (5) meal requirement for use by Caregivers and

	
Patients. Providers must recommend and assess at least one (1) patient for Obi Gen 3 in their practice setting.
 
6) Following the ~ one (1) week trial, Qualtrics will send an electronic web-based link.
 
7) Participants who complete the surveys will receive a \$25 electronic gift card
 
8) Optional: Follow-up interviews completed by telephone, if warranted, within one (1) month of survey completion.

Schedule of Events	
1) Pre-Screening
 
2) Recruitment, electronic and paper flyers
 
3) Screening (In-office assessment)
 
4) Informed Consent
 
5) ~One Week Obi Gen3 trial
 
6) Survey completion
 
7) Provide \$25 remuneration
 
8) Optional follow-up interviews

A.2. Identification and description of the Investigational Device

[figure not shown]
[figure not shown]
a) Summary Description of Investigational Device

Obi is a reusable robotic utensil intended to compensate for the function of a human arm during mealtime activities to restore a person's functional eating (self-feeding) status. Obi alleviates/ameliorates the disability caused by medical diseases/conditions that completely or severely impair the upper extremities/limbs. Obi provides a cross-cultural, broad user demographic with the ability to make decisions on what and when to eat through an easy-to-learn and use user interface.

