- e) **The follow up period during the clinical investigation shall permit the demonstration of clinical performance, effectiveness or safety over a period of time sufficient to represent a realistic test of the investigational device and allow any risks associated with adverse device effects to be identified and assessed.**

The ~one week follow-up period for this clinical investigation has been designed to allow for a realistic and contextually appropriate assessment of the Obi Gen 3 Medical Robotic Feeding Device efficacy as it relates to usability in typical use environments (e.g., home, community, or clinical settings). While the device is not intended for therapeutic intervention and poses minimal risk as a Class I medical device, the selected timeframe is sufficient to evaluate its usability, clinical performance, and user experience across diverse stakeholder groups.

The primary follow-up period consists of a ~one-week trial, during which participants (patients and caregivers) are expected to use the device across a minimum of five meal sessions. This time frame reflects common practice in assistive technology evaluation, enabling users to become familiar with the device and providing adequate exposure to assess:

- Effectiveness in supporting independent self-feeding,
- User satisfaction and ease of use,
- Integration into existing routines or caregiving workflows, and
- Identification of any usability challenges or design limitations.

f) Address what specific medical care is appropriate to be provided for the subjects after the clinical investigation has been completed, if applicable.

Specific medical care is not thought to be necessary given the device's safety history of 0 adverse events, and Class I nature.

g) Address recommended follow-up for the subjects after the clinical investigation has been completed.

When warranted, investigators may reach out within a month after the survey is completed for further clarification or expansion of open-ended survey question responses. Risks such as user fatigue, frustration, or device misuse are most likely to emerge within this timeframe. The structured follow-up, including post-trial surveys via Qualtrics and optional phone interviews, will ensure timely identification and documentation of any unexpected adverse device effects, even though none are anticipated.

h) Address the final disposition or potential future use of samples obtained from subjects, if applicable.

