Although this study does not include formal repeated-measures testing or time-stamped use logs, reported experience over multiple uses (i.e., across several meals and settings) will provide insight into how effectively users can learn to operate the device independently. This data will inform training recommendations and design refinements to support intuitive, low-burden use in real-world environments.

g) Pass/fail criteria to be applied to the results of the clinical investigation.

As a design validation study, the primary objective of this clinical investigation is to determine whether the Obi Gen 3 production equivalent device meets its formally documented user needs and intended use across three key stakeholder groups: patients, caregivers, and providers. The pass/fail criteria are based on usability outcomes aligned with ISO 13485 and FDA design validation requirements. The following criteria must be met for the device to be considered as having “passed” the clinical investigation:

Primary Endpoints: Acceptance criteria is based on safety and quality risk (see IFD-DES-054-1, Design Validation Plan, and IFD-DES-054-2, Design Validation Protocol). Note: Design Validation planning involves more than just human subject testing. This CIP covers only the human subject portion.

Intended Use: For all subjects that complete the 1-week trial, the following must be met:

- ICF performance qualifier for Functional Eating must drop at least one severity level (ex. “severe” to “moderate”) for 85% of patients.
- No Serious Adverse Device Effects (SADE), Serious Health Threat, or Unanticipated Serious Adverse Device Effect (USADE).

User Needs: For all subjects that complete the 1-week trial, 50% of respondents must be in favor that the requirement has been fulfilled (see IFD-DES-051-1 Validation Plan)

If the investigation meets or exceeds these thresholds across all stakeholder groups, the design will be deemed to have passed and is considered validated. If one or more criteria are not met, the results will be analyzed to determine if design modifications, additional training resources, or workflow adjustments are necessary prior to commercialization.

h) The provision for an interim analysis, criteria for the termination of the clinical investigation on statistical grounds, where applicable.

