Although Obi3 is a Class I device with minimal risk, the study team will monitor for any such events and report them in compliance with its SOP120, its associated D-FRM-005, Complaint Form and in accordance with ISO 14155, 21CFR812, and IRB requirements.

d) List of non-reportable adverse events, if applicable, including rationale.

Given that Obi Gen 3 is a Class I, non-invasive, robotic feeding aid, there are no anticipated adverse events inherently associated with the device under intended use. Minor discomforts such as mild user frustration or meal spillage due to unfamiliarity with controls are not considered adverse events if they resolve quickly and do not require intervention.

Rationale: These types of issues are consistent with expected variability during first-time use of assistive technology, especially in a non-clinical trial setting, and do not pose harm or risk to the participant. Such experiences will be captured in usability feedback but do not require AE reporting.

e) Time period in which the principal investigator shall report all adverse events and device deficiencies to the sponsor and, where appropriate, to ECs and the regulatory authority.

The principal investigator (PI) is responsible for reporting all adverse events (AEs), serious adverse events (SAEs), and device deficiencies to the sponsor within 24–48 hours of becoming aware of the event.

f) Details of the process for reporting adverse events (date of the adverse event, treatment, resolution, assessment of both the seriousness and the relationship to the investigational device and the related procedure).

All device deficiencies, whether or not they result in an adverse event, must be documented and reported to DESIN LLC within 48 hours of discovery. Reporting should include:

- Description of the deficiency or malfunction
- Date of occurrence
- Whether or not the deficiency led to device unavailability, user risk, or disruption of the study
- Any corrective actions taken or recommended
- Whether the deficiency was identified before or during use

The need to capture AEs is not dependent upon whether the clinical event is associated with the use of the study device or study procedure.

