Complaints regarding the device, including notice of an adverse event, or adverse device effect will be processed in accordance with DESIN LLC's SOP120, Return and Service Procedures, which include processes and timing for adverse event handling, documentation and reporting to regulatory authorities.

DESIN LLCs Service Manager will be provided a copy of the study device serial numbers in order to flag complaints resulting from the study. Any complaints, including notification of adverse events, resulting from study devices will be promptly sent to [name] & PI [name].

For the purposes of this study, all AEs/SAEs/SADEs/USADE, or Serious Health Threats (events) must be collected from enrollment (ICF signature) through study completion. The principal investigator is ultimately responsible for reporting such events to the IRB.

Events should be recorded in standard medical terminology rather than the subject's own words.

- Note the duration by entering the date of onset and date of resolution.
- Note the worse intensity of the event as mild/moderate or severe.
- Note the frequency of the event as a single episode, intermittent, or continuous.
- Note the actions taken as none, medication, procedure, or other.
- Note the relationship to study procedure or device as not-related, unlikely, possibly related, probably-related, or causal relationship.

g) Details of the process for reporting device deficiencies.

Device deficiencies, including handling of adverse events, and adverse device effects (including timeframes for reporting), will be processed in accordance with the company's complaint handling procedure, SOP120, including D-FRM-005, Complaint Form. Device deficiencies will be recorded using the Complaint form and reviewed by the quality and engineering teams for tracking and analysis.

Corrective/Preventive Action will occur in accordance with SOP080, CAPA procedures, and any advisory notices or recalls will be executed per SOP070, Non-Conformance procedures.

h) List of foreseeable adverse events and anticipated adverse device effects, together with their likely incidence, mitigation, or treatment.

There are no anticipated serious adverse events (SAEs) based on the device's classification and prior real-world use. The following are foreseeable but rare adverse device effects during use of the Obi Gen 3:

- Frustration or anxiety related to unfamiliar technology or difficulty in control coordination

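### All adverse events must be captured and zero serious device effects is a pass criterion, but the protocol fixes no point at which every patient or caregiver is asked about them

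*Protocol*

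**What the plan says.** The primary safety endpoint in the synopsis (A.1.5) is "Monitoring and recording of any adverse events through company's existing SOP120". Appendix A lists SOP120 as the return and service procedure. A.11 b) and A.14 c), f) and g) run it through the complaint form, and A.14 f) states: "Complaints regarding the device, including notice of an adverse event, or adverse device effect will be processed in accordance with" SOP120.

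The capture duty in A.14 f) is broad: "The need to capture AEs is not dependent upon whether the clinical event is associated with the use of the study device" or a study procedure, and events "must be collected from enrollment (ICF signature) through study completion".

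A.7 g) then uses safety as a pass/fail criterion. It opens with "For all subjects that complete the 1-week trial, the following must be met", and one of the two conditions is "No Serious Adverse Device Effects (SADE), Serious Health Threat, or Unanticipated Serious Adverse Device Effect (USADE").

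On how events come to light, A.6.4 g) relies on the post-trial surveys and optional telephone interviews: "The structured follow-up, including post-trial surveys via Qualtrics and optional phone interviews, will ensure timely identification and documentation of any unexpected adverse device effects". The synopsis procedure ends with "8) Optional: Follow-up interviews", and its entry on participation duration says that interviews will not be held with all participants. A.6.4 a) adds a follow-up office assessment with the provider for those who complete the trial, at which the second part of the MDNA form is filled in.

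**The concern.** A complaint procedure receives what someone decides to notify. A family that does not connect an event with the device has little reason to file a device complaint, yet A.14 f) wants that event too. The method named therefore does not match the requirement.

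The mismatch matters because the criterion is a zero count. An event that goes unreported moves the result towards a pass, and a single qualifying event would decide the criterion the other way. A.14 h) itself lists choking risk as foreseeable, and 15 of the 20 planned patients are children (A.6.3 h)). The safety history cited in A.4 c) also rests on notices received, so a study that captures events in the same way adds little to it.

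**Working it through.** **1. Where could a participant be asked?**

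- Synopsis, Schedule of Events: eight steps, none for adverse events.
- A.6.1 d), variables and timing: usability, experience, function, psychosocial impact and feedback on materials, at baseline, during the trial and post-trial. Adverse events are not listed.
- Synopsis and A.6.1 c), survey content: demographics, use experience, fulfilment of needs, SUS, modified MPT and some caregiver burden items. No adverse event item is mentioned.
- Interviews: optional, and used to clarify survey answers.
- A.6.4 a), follow-up office assessment: completers only. The MDNA form is the only content named.
- A.5 a) and A.14 c): participants or events will be monitored, with no method given. A.6.5 says that no official monitoring plan has been developed.
- A.14 e): the principal investigator reports within 24 to 48 hours of learning of an event. A.6.1 b) keeps the investigator out of direct data collection. The route described for informing the investigator is the forwarding of complaints on study devices (A.14 f)).

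None of these sets a question for every patient or caregiver. The assurance in A.6.4 g) therefore has no described content behind it.

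**2. Who is inside the criterion?** A.7 g) covers those who complete the week. A.6.3 c) i) withdraws patients who turn out unable to use the device safely or effectively, typically on the first day. An event that led to withdrawal could therefore fall outside the count.

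**3. What incomplete reporting does to a zero count.** The protocol gives no safety event rate, detection probability or bound, so there is no figure of its own to reproduce. From the protocol: n = 20 patients (A.6.3 h)), or 20 × 0.9 = 18 at the limit of the expected drop-out below 10% (A.7 e)). Assumed: a true per-patient rate p of 5% or 10%, and a share s of true events that is reported, from 0.25 to 1.

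Chance that none is recorded = (1 − p·s)^n. One-sided 95% upper bound on the true rate after zero recorded events = (1 − 0.05^(1/n)) / s.

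| s | none recorded, p = 5%, n = 20 | none recorded, p = 10%, n = 20 | none recorded, p = 10%, n = 18 | upper bound, n = 20 | upper bound, n = 18 |
|---|---|---|---|---|---|
| 1 | 36% | 12% | 15% | 13.9% | 15.3% |
| 0.8 | 44% | 19% | 22% | 17.4% | 19.2% |
| 0.5 | 60% | 36% | 40% | 27.8% | 30.7% |
| 0.25 | 78% | 60% | 63% | 55.6% | 61.3% |

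For example, p = 10%, s = 0.5 and n = 20 give (1 − 0.05)^20 = 0.358.

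Even with complete reporting, zero events in 20 patients leaves rates up to 13.9% compatible with the data. Incomplete reporting widens that bound by an amount the study cannot estimate, because it does not record who was asked.

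**The case against.** The strongest reply is that the forms are not in hand. The surveys, interview guides, MDNA form and SOP120 are separate documents. Adverse event items often sit in such forms, and A.6.4 g) says outright that the surveys will find these effects. This stands as a limit: an item cannot be ruled out. The protocol nevertheless neither requires nor cites one.

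Several stronger readings are tempting, and the documents do not support them.

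- *There is no scheduled post-trial assessment.* There is: a survey for all participants and an office assessment for completers. What is missing is a stated adverse event question at either.
- *Events have no route into the data.* Routes exist. A.14 imposes collection and reporting duties, A.8 a) admits hospital and clinic records and any adverse event note as source documents, A.6.5 gives the sponsor access to medical records, and A.6.1 h) has events documented at study end. These state duties and sources, not a way of asking each patient.
- *A silent patient is counted as event-free.* No rule says so. A.7 a) ties the analysis population to a completed survey and does not impute, and A.7 m) reports missingness for each data element. The most one can say is that a zero count does not reveal silence.
- *Drop-outs are never contacted.* A.6.3 c) ii) plans an automated reminder and up to two further attempts, and A.7 m) asks those who withdraw for a reason.
- *Participants judge relatedness.* A.14 f) sets a five-level relationship scale for recorded events and tells no participant to filter them.

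It is also fair to say that the criterion concerns serious events, which caregivers and providers may well report unprompted, so s may be near 1. Finally, A.5 a) says that no safety claims are assessed. That does not remove the point, since A.7 g) still makes zero serious device effects a condition of passing.

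**Conclusion.** The point holds in limited form. The protocol demands capture of adverse events regardless of cause and hangs a pass criterion on a zero count. The only capture procedure it describes is complaint handling, and it sets no point at which every patient or caregiver is asked. The assurance in A.6.4 g) is not borne out by the described survey content or by interviews held with only some participants. A recorded zero therefore cannot distinguish no event from no report, and any error favours a pass.

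The size is unknown. The table shows direction and sensitivity under assumed rates and reporting shares; it does not estimate under-reporting in this study. The conclusion rests on the protocol text alone and would shrink to a missing cross-reference if the forms already carry the question. It warrants a change because the change is cheap and the criterion is decisive.

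**What to change.** Specify one standard question, neutral as to cause, on any health problem, injury or illness since consent, whether or not thought to be linked to the device.

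1. Put it in the patient and caregiver post-trial surveys and in the follow-up office assessment (A.6.4 a)).
2. Ask it at early withdrawal (A.6.3 c) i), A.7 m)) and in the contact attempts already planned for non-responders (A.6.3 c) ii)).
3. Send any positive answer to the principal investigator under A.14, using the coded study number. Reconcile this with the anonymised survey responses promised in A.6.4 c), since A.8 d) provides for coded data with a master list.
4. Report the zero count over the number of exposed patients actually asked, including those withdrawn before the end of the week, and reconcile this with the restriction to completers in A.7 g).
5. Reword A.6.4 g) to match. If the forms already contain the question, cite it in A.6.4 and A.14.

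The cost is one or two items in existing Qualtrics forms and a line in the contact script. The downsides are more minor events to review and IRB approval of the changed instruments before use (A.10 c)).
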